Protocol Number: LP-CT-PALO-202002

Study Title	A Randomized, Dose-ranging, Open-label, Parallel Group Study to Assess the Efficacy, Safety and Pharmacokinetics of Palonosetron HCl Buccal Film versus IV Palonosetron 0.25 mg (ALOXI®) for the Prevention of Chemotherapy-induced Nausea and Vomiting in Cancer Patients Receiving Moderately Emetogenic Chemotherapy
NCT Number	NCT04592198
Protocol Number	LP-CT-PALO-202002
Protocol Version	2.0
Protocol Date	12 August 2020

SYNOPSIS

Study Number:	LP-CT-PALO-202002
Name of Investigational Product:	Palonosetron HCl Buccal Film (LP035)
Title of Study:	A Randomized, Dose-ranging, Open-label, Parallel Group Study to Assess the Efficacy, Safety and Pharmacokinetics of Palonosetron HCl Buccal Film versus IV Palonosetron 0.25 mg (ALOXI®) for the Prevention of Chemotherapy-induced Nausea and Vomiting in Cancer Patients Receiving Moderately Emetogenic Chemotherapy
Indication:	Prevention of acute and delayed nausea and vomiting associated with moderately emetogenic cancer chemotherapy
Development Phase:	2
Objectives:	To compare the efficacy, safety and pharmacokinetics of single dose of Palonosetron HCl Buccal Film 0.25 mg or 0.5 mg to IV palonosetron 0.25 mg in the prevention of chemotherapy-induced nausea and vomiting in cancer patients receiving moderately emetogenic chemotherapy
Study Population:	The study population will consist of male or female adult chemotherapy naïve (i.e. no history of cytotoxic chemotherapy) or non-naïve patients with histologically or cytologically confirmed solid tumors, scheduled to receive MEC.
Study Design:	This is a randomized, open-label, multicenter, parallel group, dose-ranging efficacy, safety and pharmacokinetic study. Patients will be randomized into three treatment groups.
Number of Subjects:	22 subjects will be randomized into three treatment groups, 8 subjects in 0.25 mg LP035 group, 8 subjects in 0.5 mg LP035 group, 6 subjects in 0.25 mg ALOXI® group. Palonosetron PK will be assessed in a subgroup of patients in 12 patients, 4 patients per group.
Study Duration:	Patients not included in the PK subgroups, will stay on the study for a maximum of 16 days including an up to 7-days screening period, 6 days on study (control phase) and a follow-up patient visit or telephone call 3 days after control phase. Patients involved in the PK subgroups will stay on the study for a maximum of 18 days including an up to 7-days screening period, 8 days on study (6 days control phase, and an additional 2 days PK phase) and a follow-up patient visit or telephone call 3 days after the PK phase.
Treatment Groups:	Divided into 3 groups: Test Drug (Group A): Palonosetron HCl Buccal Film 0.25 mg, administered on Day 1, 8 subjects; Test Drug (Group B): Palonosetron HCl Buccal Film 0.5 mg, administered on Day 1, 8 subjects; Reference (Group C): IV palonosetron 0.25 mg (ALOXI®), administered on Day 1 6 subjects.
Criteria for Inclusion:	For inclusion in the study, patients must fulfill all of the following criteria: 1. Provide written informed consent; 2. Male or female, aged ≥ 18 years; 3. With histologically or cytologically confirmed malignant disease; 4. Patients and patients' partners using reliable contraceptive measures;

Criteria for Inclusion:	5. Female patient of childbearing potential having a negative serum pregnancy test; 6. Be able to read, understand, and follow the study procedures and able to complete patient diary autonomously.
Exclusion Criteria:	Any of the following is regarded as a criterion for exclusion from the study: 1. Expect to be non-compliant with the study procedures; 2. Receive any investigational drugs within 30 days before the start of study treatment or schedule to receive a highly or moderately emetogenic chemotherapeutic agent; 3. Have a clinically unstable seizure disorder with seizure activity requiring anticonvulsant medication; 4. Have severe renal or hepatic impairment; 5. Have positive serology test results; 6. Have a known contraindication to 5-HT ₃ receptor antagonists; 7. Treat with commercially available palonosetron formulations within 2 weeks prior to start of study treatment or enrollment in a previous trial investigating palonosetron; 8. Is allergic to palonosetron or any other 5-HT ₃ antagonist; 9. Is currently a user of any recreational or illicit drugs (including marijuana) or has current evidence of drug or alcohol abuse or dependence as determined by the investigator; 10. Will be receiving stem cell rescue therapy in conjunction with study related course of emetogenic chemotherapy; 11. Has received or will receive total body irradiation or radiation therapy to the abdomen (includes the level of the diaphragm and below) or pelvis in the week prior to Treatment Day 1 and/or during the diary reporting period.
Study Treatments:	Test Drug (Group A): Administration of Palonosetron HCl Buccal Film 0.25 mg on Day 1, 60 ± 10 min before start of Chemotherapy. Test Drug (Group B): Administration of Palonosetron HCl Buccal Film 0.5 mg on Day 1, 60 ± 10 min before start of Chemotherapy. Reference (Group C): IV palonosetron 0.25 mg (ALOXI®) administered on Day 1, 30 ± 5 minutes before start of Chemotherapy, as an IV bolus over 30 seconds.
Schedule of Patient Visits:	Patients will undergo the following visits: 
Screening: Visit 1 (Day -7 to Day -1);Visit 2 (Day 1): chemotherapy and study drug administration;Visit 3 (Day 2): 24 hours after the start of chemotherapy administrationVisit 4 (Day 6 [+2 days]/Day 8): 120 [up to 175] hours after start of chemotherapy administrationVisit 5 (Day 9 [± 1 day]/Day 11 [± 1 day]): follow-up [visit or phone contact].
Chemotherapy Regimens:	Any MEC (ASCO Guideline), taken on Day 1 is allowed. If more than one agent considered as MEC is administered on Day 1, the start time of the first agent is to be considered as the start of chemotherapy. Any chemotherapy agent of high or moderate emetogenicity during the period from Day 2 up to 120 hours after start of chemotherapy is not allowed.

Efficacy Assessments:	
Primary Endpoint: Complete response (CR) (no emetic episode and no rescue medication) during the first 24 hours after chemotherapy.

Safety Assessments:	Safety assessments include the recording and assessing of all adverse events (AEs), vital signs, physical examinations (PE), clinical laboratory parameters, 12-lead electrocardiogram (ECG), buccal application site evaluation at 0.5 hour (for all subjects), 24 hours (for all subjects) post-dose and at Visit 4 (day 8 for PK subgroups, day 6-8 for non-PK subgroups).
Analysis Sets:	
The full analysis set (FAS) is defined as all randomized patients who received the study medication and at least chemotherapy. The analysis based on the FAS is considered as primary analysis for all efficacy parameters.
 
The per-protocol (PP) set is defined as all patients who completed Day 2 (primary endpoint) and who is compliant with the study protocol.
 
Pharmacokinetic set (PKS) is defined as all subjects completing the study and for whom the pharmacokinetic profile can be adequately characterized.
 
The safety set (SS) is defined as all patients treated and have at least one safety assessment after treatment. "Patients treated" is defined as any patient who received any study medication (palonosetron).

Pharmacokinetic:	Parameters: AUC _{0-t} , AUC _{0-inf} , C _{max} , Residual area, T _{max} , T _{1/2 el} , and k _{el} .
Statistical Methods:	
Efficacy: The primary analysis will be summarized by treatment arm. The number and proportion of patients will be presented by frequency table. For the response rate and for the difference in response rate between each Palonosetron HCl Buccal Film group and IV palonosetron group, 95% confidence interval (CI) will be provided. For the CR rate at 24 h, analyses will be carried out for both FAS and PP population; the other parameters will be analyzed only for FAS population. The subgroups will be analyzed based on FAS for the primary efficacy by age, gender, chemotherapy history, ethanol use, history of pregnancy-related morning sickness, history of motion sickness. The between-group treatment effect (with a nominal 95% CI) for the primary endpoint will be estimated within each category.
 
Safety: The analysis of safety will be performed for the safety set. The result will be interpreted in a descriptive manner. Incidence of AEs will be calculated overall, by system organ and by preferred term. Physical examination, vital signs, 12-lead electrocardiogram and application site evaluation data will be listed and summarized. For vital signs, differences will be calculated compared to baseline. Laboratory data will be analyzed and described considering the age and/or gender dependent normal ranges of the local laboratory. Laboratory data will be summarized and listed. Marked abnormalities and assessments concerning clinical relevance for abnormal values will be included. Shift tables will be used for vital signs and laboratory data to evaluate categorical changes with respect to normal ranges.

Sponsor:	Xiamen LP Pharmaceutical Co., Ltd.

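### Does the primary endpoint's 24-hour window start at the end of chemotherapy and so miss emesis during the infusion?

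*Combined protocol and SAP*

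**What the plan says.** The primary endpoint, in the Synopsis under Efficacy Assessments, is "Complete response (CR) (no emetic episode and no rescue medication) during the first 24 hours after chemotherapy". Statistical Methods refers to the same variable only by its hour: "For the CR rate at 24 h, analyses will be carried out for both FAS and PP population". Neither sentence says when the clock starts.

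The other chemotherapy-related times in the Synopsis do say so:

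- **Study Treatments:** the films are given "60 ± 10 min before start of Chemotherapy" and the IV comparator "30 ± 5 minutes before start of Chemotherapy".
- **Schedule of Patient Visits:** Visit 3 is at 24 hours, and Visit 4 at 120 (up to 175) hours, both counted from the start of chemotherapy.
- **Chemotherapy Regimens:** a further agent of high or moderate emetogenicity "during the period from Day 2 up to 120 hours after start of chemotherapy is not allowed". If several moderately emetogenic agents are given on Day 1, "the start time of the first agent is to be considered as the start of chemotherapy".
- **Analysis Sets:** the per-protocol set is "all patients who completed Day 2 (primary endpoint") and who complied with the protocol, so the endpoint is tied to Day 2.

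**The concern.** The words can be taken to mean after chemotherapy has been given. The window would then open when the infusion ends. A patient who vomited or took rescue medication during the infusion, and not afterwards, would count as a complete responder. A patient whose only event came shortly after Visit 3 would count as a failure. Since "Any MEC (ASCO Guideline), taken on Day 1 is allowed", including several agents on one day, infusion length can differ between patients, and the stretch of time scored would differ with it.

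This is the only primary endpoint, the trial is open-label and the groups are very small. An unstated time zero would matter if people scoring the diaries chose different ones.

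**Working it through.** **Inputs.** Group sizes are 8, 8 and 6 (Number of Subjects). Visit 3 is at 24 h and Visit 4 at 120 to 175 h from the start (Schedule of Patient Visits). The time T from the start to the end of Day 1 chemotherapy is not given, so the values of T below are assumptions.

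**Step 1: the plan's own conversion of hours to days.** Counting from the start of chemotherapy on Day 1, the study day is 1 plus the number of whole 24-hour periods elapsed.

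- 24 h: 1 + 1 = Day 2, as stated for Visit 3.
- 120 h: 1 + 5 = Day 6, as stated for Visit 4.
- 175 h = 7 × 24 + 7: 1 + 7 = Day 8, as stated for the end of the Visit 4 range.

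The visit schedule is therefore consistent on a clock that runs from the start.

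**Step 2: the two candidate windows.** From the start the window is [0, 24]. From the end it is [T, T + 24]. The overlap is 24 − T hours.

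| Assumed T (h) | Window from the end (h) | Omitted at front and run past Visit 3 (h) | Overlap (h) |
|---|---|---|---|
| 0.5 | 0.5 to 24.5 | 0.5 | 23.5 |
| 2 | 2 to 26 | 2 | 22 |
| 4 | 4 to 28 | 4 | 20 |
| 8 | 8 to 32 | 8 | 16 |

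For T from 0.5 to 4 h, the omitted share of the first 24 hours is 0.5/24 = 2.1% to 4/24 = 16.7%. On the start-based reading the omission and the overrun are both zero for every T.

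**Step 3: who would be reclassified.** Only two kinds of patient change status: those whose only events fall in the first T hours, and those whose only events fall between 24 and 24 + T hours. The two changes go in opposite directions. One such patient moves the rate by 1/8 = 12.5 points in a film group or 1/6 = 16.7 points in the IV group. These figures are simply 1/n and apply to any single misclassified patient. They do not say how often this would happen, and nothing in the documents allows that to be estimated.

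**Step 4: which reading the text supports.** The Chemotherapy Regimens entry, directly before the endpoint, says which start time to use when there are several agents. A visit is placed at exactly 24 h from the start, and the analysis is labelled as the rate at 24 h. No sentence gives the end of chemotherapy as a time point, so an end-based endpoint would be the only item in the Synopsis on that clock. The Day 2 link in the per-protocol definition agrees with the start-based reading but does not settle it alone, since after a short infusion an end-based window could also close on Day 2.

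**The case for a change.** The best case for acting is that intent is not text. The endpoint does not use the defined term, so the rule about the first agent does not formally reach it. That rule also covers only patients given more than one moderately emetogenic agent. The Synopsis has another 24-hour clock as well: the application-site evaluation is timed from dosing. A few words would remove the doubt at almost no cost, and in an open-label trial a primary endpoint should not depend on inference.

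The omission itself stands: no sentence states the time zero. The consequences are weaker.

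- The post-dose clock belongs to a local safety check and does not compete for the efficacy window.
- Running past Visit 3 need not lose events, because patients complete their own diary and the control phase lasts 6 days.
- Treatment is randomized and nothing suggests that infusion length differs systematically by group. Chance imbalance among 22 patients is possible but has not been shown.
- Inconsistent scoring between staff is conjecture. The available text is a synopsis and does not contain the diary instructions or the rules for deriving complete response.

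**Conclusion.** The concern identifies a real gap in wording but not a fault in the plan. The end-of-infusion window is one possible reading of an incomplete phrase, and the one that fits the rest of the Synopsis worst. Analysts would fill the gap with 0 to 24 hours from the start of chemotherapy, taking the first agent where there are several. That matches Visit 3 exactly and needs no extra data, so writing it down would leave the conduct and conclusions of the trial as they are.

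The shift of 0.5 to 4 hours depends on an assumed infusion length and arises only on the reading rejected here. The same holds for the 12.5 or 16.7 points per reclassified patient. This conclusion assumes that the diary and derivation rules, which are not in the available text, use the same start-based clock as the visits. If they explicitly counted from the end of chemotherapy, the point would need to be reopened.

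### No pre-dose buccal site evaluation is listed, so a lesion already visible at 0.5 h cannot be reliably classed as new or pre-existing

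*Combined protocol and SAP*

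**What the plan says.** **Timing.** The Safety Assessments entry of the Synopsis lists "buccal application site evaluation at 0.5 hour (for all subjects), 24 hours (for all subjects) post-dose and at Visit 4", and dates Visit 4 as "day 8 for PK subgroups, day 6-8 for non-PK subgroups". Under Study Treatments, the lower-dose film is described as "Administration of Palonosetron HCl Buccal Film 0.25 mg on Day 1, 60 ± 10 min before start of Chemotherapy"; the higher-dose film has the same timing. Every listed site evaluation thus comes after the film. The Schedule of Patient Visits includes a screening visit in the week before Day 1 and a Day 1 visit at which dosing takes place, but no site evaluation is assigned to screening or to the pre-dose part of Day 1.

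**Analysis.** Under Statistical Methods, Safety: "Physical examination, vital signs, 12-lead electrocardiogram and application site evaluation data will be listed and summarized". Comparison with an earlier state is planned for other data only: "For vital signs, differences will be calculated compared to baseline", and "Shift tables will be used for vital signs and laboratory data to evaluate categorical changes with respect to normal ranges".

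**Population.** The Study Population entry admits "adult chemotherapy naïve (i.e. no history of cytotoxic chemotherapy) or non-naïve patients". None of the 11 exclusion criteria concerns the mouth or oral mucosa.

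**Physical examination.** It is listed as a safety assessment, without timing and without mention of the mouth.

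**The concern.** Local tolerability is the safety question specific to a buccal film. The 0.5 h look is the most informative one for that question, because in the film arms it falls after the film and before that day's chemotherapy. At 24 h and at Visit 4, chemotherapy is a competing explanation for a mucosal finding. Yet the 0.5 h reading is the one with nothing before it to be compared with.

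Patients who have already had chemotherapy may arrive with mucosal lesions, and the listed criteria do not keep them out. If such a lesion is recorded at 0.5 h, the planned data do not show whether the film caused it. The trial is open-label, so attribution would rest on the judgement of staff who know the arm. With 8 patients per film arm, one or two such lesions would visibly change the local-tolerability summary that is carried forward from a dose-ranging study.

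**Working it through.** There is no planned figure to reproduce: the documents give no expected rate of site reactions and no precision target for them.

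**1. Where the 0.5 h check falls.** The film is given 60 ± 10 min before chemotherapy. The check 30 min after the film is therefore between 50 − 30 = 20 min and 70 − 30 = 40 min before chemotherapy starts.

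**2. What each planned look can settle for one patient.**

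| Pattern | What the planned data show |
|---|---|
| Absent at 0.5 h, present at 24 h or Visit 4 | New since 0.5 h; cause open between film and chemotherapy |
| Present at 0.5 h | New or pre-existing: not determined |
| Present at 0.5 h, worse later | Worsening is shown; the starting state is not |

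The gap therefore concerns lesions already visible at 0.5 h.

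**3. Weight of one misattributed lesion.** Group sizes from the Synopsis are 8, 8 and 6 (total 22). If the rate is the proportion of patients with a finding, one patient wrongly counted adds 1/8 = 12.5 points in a film arm.

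**4. How often a pre-existing lesion would be present.** Let q be the proportion of patients with a lesion at the site before dosing. The documents do not give q, so 5% to 20% is an assumed range. The chance of at least one among n patients is 1 − (1 − q)^n.

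| q (assumed) | At least one in 8 | At least one in 16 | None in 6 IV patients |
|---|---|---|---|
| 5% | 34% | 56% | 74% |
| 10% | 57% | 81% | 53% |
| 20% | 83% | 97% | 26% |

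For example, at q = 10%: 1 − 0.9^16 = 1 − 0.185 = 0.815. These are chances that a pre-existing lesion is present. Misattribution also requires that the lesion be recorded as a film reaction, so for a given q they are upper bounds.

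**5. Whether the IV arm can stand in for a baseline.** The 0.5 h and 24 h evaluations are stated to be for all subjects, so the IV patients, who receive no film, supply a concurrent background rate.
- With 0 of 6 affected, the exact two-sided 95% upper limit is 1 − 0.025^(1/6) = 45.9% (one-sided 95%: 1 − 0.05^(1/6) = 39.3%).
- Against 0 of 6, a two-sided Fisher exact p below 0.05 needs findings in at least 9 of 16 film patients, or 5 of 8 in one dose group.

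The safety analysis is descriptive and plans no such test; the figures only show how little six patients can exclude.

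**The case against.** **Only a synopsis is available.** It gives no times for vital signs, laboratory tests, ECG or physical examination, and it uses a baseline for vital signs that it never schedules. It plainly does not list every baseline measurement. A reader might infer that nobody looks at the mouth before dosing; the documents do not establish that. This stands as a limit on certainty. Against it, the site evaluation is the one safety assessment whose times are spelled out, down to PK and non-PK subgroups, and no pre-dose time is among them.

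**The physical examination may cover the mouth.** It may, and it may be done on Day 1. The text states neither timing nor oral content, so it can be neither relied on as a baseline nor dismissed as out of date.

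**The trial is randomised and has a control arm.** Pre-existing lesions are expected equally in all arms, so they add noise rather than systematic bias to any contrast between the two film doses. A reader might infer that this contrast is biased; the design does not support that, and no formal comparison of site rates is planned. The point stands at group level. But six controls give little precision, and no parallel arm can tell whether a given patient's lesion was already there, which matters when 22 patients are reviewed descriptively.

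**Later lesions are not ambiguous in this way.** Correct: one absent at 0.5 h was not there before dosing. It would be too broad to say that film reactions in general cannot be told apart from earlier lesions.

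**Conclusion.** The concern holds in a limited form. Followed as written, the synopsis provides no pre-dose reading of the application site and no baseline comparison for it, so a lesion already visible at 0.5 h cannot be reliably classed, for an individual patient, as new or pre-existing.

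The cost of each error is 12.5 points in an 8-patient film arm. The 56%, 81% and 97% figures rest on assumed site prevalences of 5%, 10% and 20% and independence between patients, and they bound misattribution from above. Prevalence at the film site would not exceed prevalence anywhere in the mouth, so the lower part of the range may be the more relevant.

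The primary efficacy analysis is not affected. The point is worth acting on because a pre-dose state that was not recorded cannot be recovered once the film has been applied. If the fuller protocol or the case report form already contains a pre-dose evaluation of the same site, only the synopsis and the analysis text need to change.

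**What to change.** - **Assessment.** Add the application site evaluation before dosing on Day 1, for all subjects, on the same form and scale as the 0.5 h evaluation. Using the same assessor at both times is preferable but not essential. If such an evaluation already exists elsewhere, list it with the other times under Safety Assessments.
- **Analysis.** Under Statistical Methods, Safety, state that application-site findings will be summarised by arm and time point as new or worsened relative to pre-dose, with pre-existing findings listed separately.
- **Limits.** If the physical examination is meant to serve as the baseline, state its timing and that it includes the application site on the same scale.

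The cost is a brief visual check and one more form entry at a visit the patient already attends. The downside is a short addition to Day 1. Sample size, visit schedule and efficacy analysis are unchanged.

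### The supportive per-protocol set requires completion of Day 2, so it can drop a patient already known to have failed the 24-hour endpoint, which raises that arm's PP response rate

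*Combined protocol and SAP*

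**What the plan says.** - **PP set** (Synopsis, Analysis Sets): "all patients who completed Day 2 (primary endpoint) and who is compliant with the study protocol". No exception is given for a patient whose outcome is already settled, and compliance is not defined further.
- **Primary endpoint** (Synopsis, Efficacy Assessments): "Complete response (CR) (no emetic episode and no rescue medication) during the first 24 hours after chemotherapy".
- **Timing** (Synopsis, Schedule of Patient Visits): Day 2 is Visit 3, placed 24 hours after chemotherapy starts.
- **FAS** (Synopsis, Analysis Sets): "all randomized patients who received the study medication and at least chemotherapy". There is no completion requirement. On its status the plan says: "The analysis based on the FAS is considered as primary analysis for all efficacy parameters".
- **Use of the two sets** (Synopsis, Statistical Methods): "For the CR rate at 24 h, analyses will be carried out for both FAS and PP population". Other efficacy parameters and the subgroups use the FAS only.
- **Arm sizes** (Synopsis, Number of Subjects): "8 subjects in 0.25 mg LP035 group, 8 subjects in 0.5 mg LP035 group, 6 subjects in 0.25 mg ALOXI® group".

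The available text has no rule for a patient who withdraws before the 24-hour assessment.

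**The concern.** Membership of the PP set depends on an event after randomisation that can be related to the outcome. CR needs 24 event-free hours, so nobody can be a confirmed responder before the window closes. Failure can be confirmed within hours. Among patients whose outcome is settled before Visit 3, all are therefore failures, and a completion rule that removes any of them removes failures only.

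The 24-hour CR rate is the one parameter analysed in the PP set, as a companion to the FAS result. If the PP set discards documented failures, its CR rate partly reflects who stayed until Visit 3. With arms of 8, 8 and 6, a single patient is enough to be visible in the reported rate and in the comparison with IV palonosetron.

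**Working it through.** The plan states no assumed CR rate, withdrawal rate, power or margin, so there is no figure of its own to reproduce here. The arm sizes agree with the stated total: 8 + 8 + 6 = 22. I take the 24-hour window to run from the start of chemotherapy, to match Visit 3.

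**1. Does the rule remove a known failure?** Take a patient who vomits at hour 4 and withdraws at hour 10. By the endpoint definition this patient is a failure from hour 4. The patient has not reached Visit 3, so has not completed Day 2 and is outside the PP set. The same patient received study drug and chemotherapy, so is in the FAS as a non-responder.

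**2. Size of one removal.** With r responders among n patients, removing one failure changes the rate from r/n to r/(n-1), a rise of r/[n(n-1)]. This is positive whenever r > 0. The values of r are assumptions.

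| n | r | All kept | One failure removed | Rise (points) |
|---|---|---|---|---|
| 8 | 4 | 4/8 = 50.0% | 4/7 = 57.1% | 7.1 |
| 8 | 5 | 5/8 = 62.5% | 5/7 = 71.4% | 8.9 |
| 8 | 6 | 6/8 = 75.0% | 6/7 = 85.7% | 10.7 |
| 8 | 7 | 7/8 = 87.5% | 7/7 = 100% | 12.5 |
| 6 | 3 | 3/6 = 50.0% | 3/5 = 60.0% | 10.0 |
| 6 | 4 | 4/6 = 66.7% | 4/5 = 80.0% | 13.3 |
| 6 | 5 | 5/6 = 83.3% | 5/5 = 100% | 16.7 |

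With fewer responders than half the arm, the rise is smaller.

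**3. Film minus IV.** Assume film 6/8 and IV 4/6.

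- All kept: 75.0 - 66.7 = +8.3 points.
- One film failure removed: 85.7 - 66.7 = +19.0 points.
- One IV failure removed: 75.0 - 80.0 = -5.0 points.

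The direction depends on which arm loses the patient.

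**4. Set against precision.** The plan says a "95% confidence interval (CI) will be provided" but names no method in the available text; I used exact Clopper-Pearson intervals. For a film arm, 6/8 gives 34.9-96.8% and 6/7 gives 42.1-99.6%. For the IV arm, 4/6 gives 22.3-95.7% and 4/5 gives 28.4-99.5%. The shift is small beside the width of these intervals.

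**5. In expectation.** Let p be the true CR rate and q the share of failures who leave before completing Day 2. The expected PP rate is approximately p / [1 - (1-p)q]. Both p and q are assumptions.

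| p | q = 5% | q = 10% | q = 30% |
|---|---|---|---|
| 50% | 51.3% (+1.3) | 52.6% (+2.6) | 58.8% (+8.8) |
| 80% | 80.8% (+0.8) | 81.6% (+1.6) | 85.1% (+5.1) |

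At q = 5-10% the expected shift is 0.8 to 2.6 points, or about 1-3.

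**The case against.** The strongest reply is that the plan already protects the main result. The FAS is primary for every efficacy parameter, has no completion requirement and keeps the patient described. No test or margin depends on the PP set. This stands, and it limits the point to a supportive analysis.

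Second, the event may be rare. Study drug is given once, the window is 24 hours, and nothing in the text makes rescue use a reason for withdrawal. This also stands. Assuming that 25-50% of failures leave early would make a true 80% read 84-89% and a true 70% read 76-82%, but the documents give no basis for that range.

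Third, the parenthesis after Day 2 may be meant as primary endpoint assessed, which would keep a documented failure in the set. That is possible, but the text does not say it. If it is the intention, the fix only writes it down. Only a synopsis is available, so a fuller definition elsewhere cannot be checked.

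Three stronger readings are tempting and are not supported:

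- **That the PP rate can only exceed the FAS rate.** The upward direction belongs to this mechanism alone. The PP set also excludes non-compliant patients, who may be responders: removing one responder from 6/8 gives 5/7 = 71.4%, which is lower than 75.0%.
- **That agreement between FAS and PP would tell the reader nothing.** Dropping such a patient makes the two sets disagree (7/8 against 7/7). Barring an offsetting exclusion, agreement suggests that it did not happen.
- **That the open-label design biases the comparison in favour of the film.** Withdrawal could differ by arm, but no document says that it would or in which direction.

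**Conclusion.** The point holds for the PP analysis of 24-hour CR. On its plain reading the rule excludes a patient who is a known failure but leaves before Visit 3, and each such exclusion raises that arm's PP rate when the arm has at least one responder. One patient is worth about 7 to 12.5 points in an arm of 8 and about 10 to 17 points in the arm of 6, given that at least half the arm responds. The film minus IV difference can shift in either direction.

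The effect is conditional on such a patient occurring. The expected shift of about 1-3 points rests on an assumed 5-10% of failures leaving early and a true CR of 50-80%; the documents supply neither figure. A reader might infer that the trial's primary result is inflated. It is not, because the FAS keeps these patients. This is a modest defect in a supportive set, worth correcting because the correction is simple.

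**What to change.** Define the PP set as FAS patients who comply with the protocol and whose 24-hour CR status is known. Add that any patient with an emetic episode or rescue medication within 0-24 hours counts as a non-responder in the PP set, whether or not Day 2 was completed.

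In the examples above this restores 6/8 (75.0%) in place of 6/7 (85.7%), and 4/6 (66.7%) in place of 4/5 (80.0%). A patient who leaves event-free before 24 hours has unknown status and would stay outside the PP set.

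The cost is a sentence or two in the analysis-set definition. No data collection is added and the FAS is unchanged. The PP CR rate may be slightly less favourable.

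### The study-completion condition in the PK set can only exclude patients whose profile is already adequate, and deleting it would protect data in groups of 4

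*Combined protocol and SAP*

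**What the plan says.** Under Analysis Sets, the synopsis defines the PKS as "all subjects completing the study and for whom the pharmacokinetic profile can be adequately characterized". A patient must meet both conditions. The text supplied does not define completion.

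Study Duration describes time on study for PK patients in two ways:

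- Total span: these patients "will stay on the study for a maximum of 18 days including an up to 7-days screening period, 8 days on study", followed by "a follow-up patient visit or telephone call 3 days after the PK phase". The 18-day total counts the follow-up.
- On-study period: "8 days on study (6 days control phase, and an additional 2 days PK phase". This ends on Day 8, and the follow-up is listed separately.

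Safety Assessments places Visit 4 at "day 8 for PK subgroups, day 6-8 for non-PK subgroups". Schedule of Patient Visits gives Visit 5 for PK patients as Day 11 ± 1 and describes it as "follow-up [visit or phone contact". Number of Subjects puts 12 patients in the PK subgroup, 4 per group.

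No other analysis set requires completing the study. The full analysis set is "all randomized patients who received the study medication and at least chemotherapy". The safety set needs treatment and one later safety assessment. The per-protocol set names Day 2 as its completion point and adds general protocol compliance.

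**The concern.** An analysis set for PK should turn on whether the patient was dosed and whether the concentrations support the parameters. The second half of the PKS definition already asks the latter. The first half asks about participation in the study, and because the two are joined by a logical and, it has an effect only when a profile has passed the adequacy test and would otherwise be analysed.

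The stake is small but real. Pharmacokinetics is one of three stated objectives and rests on 4 patients per group, so one excluded profile is a quarter of a group. On the wider reading of completion, the trigger could be an unanswered telephone call after the PK phase has ended.

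**Working it through.** **Step 1. Reproduce the plan's own figures (Study Duration, Number of Subjects).**

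- PK patients: 7 (screening) + 8 (on study) + 3 (follow-up) = 18 days, as stated.
- Other patients: 7 + 6 + 3 = 16 days, as stated. The synopsis says they "will stay on the study for a maximum of 16 days including an up to 7-days screening period, 6 days on study (control phase") with follow-up 3 days later. The difference of 2 days is the PK phase.
- PK subgroup: 3 groups × 4 = 12, as stated.

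Both totals need the 3 follow-up days to add up, which supports a wide reading of completion. They also count screening, so they may describe only the span of participation.

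**Step 2. Locate the two candidate end points.**

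- Narrow: Day 8, which is Visit 4 for PK patients. The visit schedule allows up to 175 hours; 7 × 24 = 168, so hour 175 falls on Day 8.
- Wide: Visit 5, Day 11 ± 1, that is Day 10 to Day 12, or 2 to 4 days after Day 8.

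**Step 3. Apply the definition to each kind of PK patient.**

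| PK patient | Profile adequate? | Completion = Visit 5 | Completion = Day 8 | Condition deleted |
|---|---|---|---|---|
| Seen at Visit 4, reached at Visit 5 | Yes | In | In | In |
| Seen at Visit 4, Visit 5 missed | Yes | **Out** | In | In |
| Left before Day 8 | Yes | **Out** | **Out** | In |
| Any of these | No | Out | Out | Out |

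The completion condition changes membership only in the bold cells, and in each of them the profile is adequate. A patient with an inadequate profile is out under every version.

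**Step 4. What one lost profile would do to precision (illustration only).** Take a difference between two group means with a common SD, and compare 4 v 4 with 3 v 4.

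- Standard error ratio: √[(1/3 + 1/4) / (1/4 + 1/4)] = √(0.5833/0.5) = 1.080.
- 95% half-width in SD units, variance pooled over three groups: t(0.975, 9) × √(1/2) = 1.600 becomes t(0.975, 8) × √(7/12) = 1.761; ratio 1.101.
- The same from the two groups alone: t(0.975, 6) × √(1/2) = 1.730 becomes t(0.975, 5) × √(7/12) = 1.963; ratio 1.135.

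The ratios need no assumed variability. They describe losing any PK patient for any reason, in an interval that the synopsis does not say will be computed. No rate of missed follow-up is given, so the expected loss from this condition cannot be calculated.

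**The case against.** The strongest reply is that only a synopsis is available, and it is plainly abridged. It gives no PK sampling times and no PK statistical methods, and it mentions other efficacy parameters without listing them. A fuller text may define completion at Day 8, and a missed Visit 5 would then cost nothing. This stands as a limit. A reader might infer that the plan does exclude patients who miss the Day 11 contact, or that the trial has no definition of completion. The documents support neither, because the on-study period is also described as ending on Day 8 and the synopsis cannot show what a fuller text contains. The point does not depend on that question: on the Day 8 reading, the condition can still exclude an early leaver whose profile is adequate.

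A second reply is that, on the Day 8 reading, completion has some bearing on data quality. Staying through the PK phase is relevant to the terminal-phase parameters that the synopsis lists (AUC0-inf, residual area, T1/2 el and kel). This is fair, and it would be wrong to call the condition irrelevant to usability. But a profile too short for those parameters is already a matter for the adequacy condition, so completion adds nothing there except exclusions of profiles that pass.

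A third reply is that deletion leaves membership resting wholly on adequacy. That is true, but adequacy is required now as well, so no inadequate profile enters.

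Lastly, the comparison with the other sets should not be pressed too far. Protocol compliance in the per-protocol set is also an open condition and could reach Visit 5.

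**Conclusion.** The point holds as a minor improvement, not as a demonstrated error. The definition itself shows that the completion condition can only exclude adequate profiles. If completion includes Visit 5, each missed contact by a patient with an adequate profile removes a usable profile from a group of 4. If completion ends on Day 8, the loss from a missed Visit 5 is zero, and only adequate early leavers are affected.

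This assumes that PK sampling is over by Day 8. The synopsis gives no sampling times, so that is inferred from the length of the PK phase and from Visit 5 being allowed by telephone.

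A reader might take the 8% rise in standard error, or the 10% to 13% wider interval, as the cost of this condition. The documents do not support that: they give no loss rate, PK confidence interval or PK decision rule. No stated conclusion is shown to change, and the primary efficacy analysis in the full analysis set is unaffected.

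**What to change.** Delete the completion condition. The PKS would then be every PK-subgroup patient who received palonosetron and who meets the adequacy condition as it now stands. This settles the Visit 5 question and keeps early leavers whose profiles are adequate.

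As second best, keep a completion condition but tie it to the last scheduled PK sample. That removes the dependence on Visit 5, but it could still exclude a patient who misses that sample and has an adequate profile.

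Either change is one sentence and needs no new data, visits or patients. It should be made before the PK data are reviewed. If adequacy is judged parameter by parameter, the number of patients may differ between PK parameters, and the tables should show it.
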